3.3 Duration of Participation and Overview of What is Expected from Participants

Participants will complete up to a seven week study consisting of screening period, baseline period, up to a 21-day product use period with a total of 9 product use sessions. Screening assessments, baseline questions, product use period questionnaires, adverse event reporting, and end of study experience survey data will be collected. This study will be conducted remotely and will use a web-based data collection platform, Consumer Health Learning and Organizing Ecosystem (Chloe), by People Science where participants will complete study assessments using the Chloe app during the course of the study. Participants will receive the study product during the baseline period. Demographic and medical history data will be collected for the study.

3.4 Participant Recruitment

Participants will be recruited through the People Science community, People Science website, email outreach and social media channels, in addition to Phylos' community network. Local dispensaries may also be used for recruitment purposes, as deemed appropriate by Phylos and People Science. Advertisements will be in digital format and will link to a study landing page to enable sign up.

Interested individuals will have already made the decision to try these cannabinoid products.

4.0 STUDY ACTIVITY CALENDAR

Table 4.1 Study Calendar

| Protocol Activities | Screening ^(a) | Baseline ^(b) | Study Duration | | | | | | | | |
|---|--------------------------|-------------------------|---|-----------------------|------------------------------------|---|-----------------------|------------------------------------|---|-----------------------|---|
| | | | Product Use Period 1 ^(c) (Up to 7 Days) | | | Product Use Period 2 ^(c) (Up to 7 Days) | | | Product Use Period 3 ^(c) (Up to 7 Days) | | |
| | Up to Day -14 | Up to Day 14 | Product Use Session 1 | Product Use Session 2 | Product Use Session 3 / Cross-Over | Product Use Session1 | Product Use Session 2 | Product Use Session 3 / Cross-Over | Product Use Session1 | Product Use Session 2 | Product Use Session 3 / End of Study ⁽ⁱ⁾ |
| Informed Consent | X | | | | | | | | | | |
| Medical History | X | | | | | | | | | | |
| Demographics | X | | | | | | | | | | |
| Concomitant Medications | X | | | | | | | | | | |
| Eligibility Confirmation | X | | | | | | | | | | |
| Product Delivery Receipt | | X | | | | | | | | | |
| Randomization ^d (Study Product, THC Only Product, or Placebo Group) | | X | | | | | | | | | |
| MEFA Questionnaire ^e | | X | | | X | | | X | | | X |
| Daily Product Use Survey ^f | | | X | X | X | X | X | X | X | X | X |
| Adverse Event Survey ^g | | | X | X | X | X | X | X | X | X | X |
| Cross-Over ^h (Study Product, THC Only, or Placebo Group) | | | | | X | | | X | | | |
| Experience Survey | | | | | | | | | | | X |

- a. Screening activities to occur within 14 days prior to Baseline (Day -14).
- b. Baseline activities to occur up to 14 days prior to study product use sessions (Day 14).
- c. Study duration to take place up to 21 days total across 7 days maximum within 3 periods.
- d. Participants to be randomized into the Study Product, THC-Only Product, and Placebo groups for each Product Use Period.
- e. MEFA (Motivation, Energy Level, Focus, and Appetite) Questionnaire to be administered during Baseline and at the end of Product Use 3 sessions.
- f. Daily Product Use Surveys to be administered at the end of each product use session.
- g. Any adverse event occurrence to be reported after the product use session.
- h. Participants cross-over into either Study Product, THC-Only Product, or Placebo group upon completion of Product Use Period 1 and 2.
- i. Participants to complete an experience survey at the end of the study.

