6.0 STUDY PROCEDURES

6.1 Study Overview

Upon initial qualification, the participant will receive an email with study onboarding information including instructions to complete study assessments, as required. These study assessments can be accessed via the Chloe mobile app available on Apple iOS and Android devices. The participant's activities are as follows:

Screening Day -14 to Day 0:

- Complete the Informed Consent
- Complete Demographics, Medical History and Concomitant medications, including current cannabis use information (frequency, route, any previous adverse reactions from taking cannabis and tolerance in taking at least 5mg THC previously)
- Eligibility Confirmation and Enrollment

Baseline Day 1 to Day 14:

- Provide preferred delivery address for product delivery during Baseline
- Random assignment to either Study Product, THC-Only Product, or Placebo Group
- MEFA Questionnaire
- Receipt of study products within 2 weeks of eligibility confirmation
 - Participants will be asked daily if they have received their study product delivery
 - Once they confirm receipt, they will be advised on the product use period start date

Product Use Period (Up to 21 days):

- *The Participant will be randomized into either Study Product, THC-Only Product, or Placebo Group upon enrollment*

- *The Participant will be crossed-over twice into the Study Product, THC-Only Product, or Placebo Group once they have completed 3 product use sessions during the first and second product use periods*
- *The Participant will complete a total of 9 product use sessions between Study Product, THC-Only Product, and Placebo groups across a maximum of 21 days*
- *The Study Product will contain 10mg THCV + 5mg THC in the form of a single gummy.*
- *If the participant cannot tolerate or is not comfortable with 10mg THC based on cannabis use information collected at screening, the participant may opt to cut the gummy in half and be advised to use the same dose for all product use days for the duration of the study.*

Period 1: Up to 7 days

- After 3 product use sessions:
 - Daily survey questions regarding motivation, level of energy, focus and appetite
 - At the end of Period 1:
 - MEFA Questionnaire and Adverse Event Reporting

Crossover:

- Upon completion of Period 1, participants will cross-over to either the Study Product, THC-Only Product, or Placebo group for up to 7 days.

Period 2: Up to 7 days

- After 3 product use sessions:

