 - Daily survey questions regarding motivation, level of energy, focus and appetite
 - At the end of the Period 2:
 - MEFA Questionnaire and Adverse Event Reporting

Crossover:

- Upon completion of Period 2, participants will cross-over to either the Study Product, THC-Only Product, or Placebo group for up to 7 days.

Period 3: Up to 7 days

- After 3 product use sessions:
 - Daily survey questions regarding motivation, level of energy, focus and appetite
 - At the end of the Period 3:
 - MEFA Questionnaire and Adverse Event Reporting

End of Study:

- Experience Survey
- Adverse Event Reporting

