9.3 Evaluable Participants

Participants will be considered evaluable for analysis if they complete all assessments in at least two product use sessions within each group of the study.

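### Allocation to product order is worded inconsistently, does not secure each product once per participant, and is not balanced over periods

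*Combined protocol and SAP*

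**What the plan says.** The plan describes the allocation in several places, and they do not agree.

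- **Section 4.0, Table 4.1.** Randomization is marked once, in the Baseline column. Cross-Over is a separate row, marked at the third session of Periods 1 and 2.
- **Table 4.1, footnote d:** "Participants to be randomized into the Study Product, THC-Only Product, and Placebo groups for each Product Use Period".
- **Table 4.1, footnote h:** "Participants cross-over into either Study Product, THC-Only Product, or Placebo group upon completion of Product Use Period 1 and 2".
- **Section 6.1, on randomisation.** Random assignment is listed under Baseline, and the product use text adds: "The Participant will be randomized into either Study Product, THC-Only Product, or Placebo Group upon enrollment".
- **Section 6.1, on the cross-overs:** "The Participant will be crossed-over twice into the Study Product, THC-Only Product, or Placebo Group". The text after Period 2 offers the same three destinations as the text after Period 1: "Upon completion of Period 2, participants will cross-over to either the Study Product, THC-Only Product, or Placebo group for up to 7 days".
- **Section 6.1, on the total:** "The Participant will complete a total of 9 product use sessions between Study Product, THC-Only Product, and Placebo groups".
- **Section 9.3.** A participant is evaluable "if they complete all assessments in at least two product use sessions within each group of the study".

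The documents give no list of product sequences, allocation ratio, blocking or randomisation method. Section 9.6 plans linear mixed models with age and sex as the covariates fixed in advance. It names neither period nor sequence.

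**The concern.** The primary endpoint in Section 1.0 compares cannabinoid products with placebo within participants, so it depends on how products are assigned to periods. Two things are left open.

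The first is whether every participant is scheduled for all three products. Anyone who is not can never meet the rule in Section 9.3. Footnote d suggests an assignment at each period, and the cross-over wording does not limit the next product to one not yet used. Whoever programs the allocation has to choose between that text and the single Baseline mark.

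The second is the order of the products. Even if each is used once, nothing keeps a product from falling more often in early or late periods. Self-rated motivation in an app may drift over up to 21 days. Without balanced orders or a period term, part of that drift enters the product contrast.

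**Working it through.** **Inputs from the documents.** About 58 participants (Sections 3.1 and 9.2) and about 50 evaluable (Sections 9.1 and 9.2). From Section 9.6: mean change 1 point, SD 2, two-sided 0.05, Wilcoxon signed-rank, at least 90% power.

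**Assumptions, not in the documents.** Probability 1/3 per product at any fresh draw, and a drift of 0.5 points per period.

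**1. The plan's own power.** The standardised effect is 1/2 = 0.5. Power is taken from the noncentral t with n multiplied by the signed-rank efficiency 3/π = 0.955.
- n = 50: 92.3%
- n = 58: 95.5%

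The stated figure of at least 90% is reproduced. Section 9.6 frames it as a pre-use to post-use change. It serves here only to show what a loss of evaluable participants would cost at the plan's own effect and SD.

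**2. What the literal wording permits.** Three periods with three possible products give 3 × 3 × 3 = 27 sequences, of which 3! = 6 contain all three products.

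| Reading | Share with all three products | Expected of 58 | Power at that n | Randomised to expect 50 |
|---|---|---|---|---|
| Independent draw each period | 6/27 = 22.2% | 12.9 | 36% (n = 13) | 50 ÷ (6/27) = 225 |
| Previous product barred, nothing more | 6/12 = 50% | 29 | 72% (n = 29) | 50 ÷ 0.5 = 100 |
| Each product exactly once | 100% | 58 | 95% (n = 58) | 50 |

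The 12 in the second row is 3 × 2 × 2. All rows are before dropout. The binomial chance that at least 50 of 58 receive all three products is about 6 × 10⁻²⁵ in the first row and about 8 × 10⁻⁹ in the second.

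**3. Order imbalance if each product is used once.** Suppose the six orders are drawn by simple, unblocked randomisation. For two given products, the difference in period position within a person is ±1 in four orders and ±2 in two.
- Variance per person: (4 × 1 + 2 × 4)/6 = 2.
- SD of the mean difference at n = 58: √(2/58) = 0.186 periods.
- Mean absolute imbalance: 0.186 × √(2/π) = 0.15 periods.
- Resulting error at the assumed drift: 0.15 × 0.5 = about 0.07 points, against a target effect of 1 point.
- At n = 50 the SD is √(2/50) = 0.20 and the mean absolute imbalance 0.16, so the error is about 0.08 points.

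This error has expectation zero. In the same setting there is about a 35% chance (simulation) that some order receives 5 or fewer of the 58 participants.

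**4. With blocks of six.** 58 = 9 × 6 + 4, so four orders have 10 participants and two have 9.

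**The case against.** The strongest reply is that the intent is clear. Randomization has one mark, at Baseline, and Section 6.1 ties it to enrolment. Footnote d joins the three products with *and*; only footnote h and Section 6.1 offer them as alternatives. Two cross-overs and nine sessions shared among three groups, with evaluability required in each group, describe an ordinary three-period crossover. Footnote d can then be read as one Baseline act that assigns a product to every period. This stands as to intent. It does not supply the missing rule: no sentence excludes a repeat or says how orders are chosen.

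A reader might infer that most participants will in fact miss a product. The documents do not support that. The 22% and 50% show what the wording allows under equal probabilities, which the plan does not state.

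A reader might also infer a sizeable systematic bias from drift, for example 0.25 points if two products differ by 0.5 in mean period position. Under simple randomisation to six orders, a gap that large for a given pair has probability 0.8% at 58 participants and 1.4% at 50. Chance imbalance adds noise, not systematic bias. Systematic bias would need non-random orders, and no passage describes those.

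Finally, Section 9.6 allows further covariates to be chosen with directed acyclic graphs, so a period term could still enter the model. That is true, but it is not prespecified.

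**Conclusion.** The point holds as an inconsistent and incomplete allocation rule in a trial whose evaluability definition depends on that rule. It does not show that products will be repeated.

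The size depends on how the text is implemented. A literal build would leave about 13 or 29 of 58 participants able to become evaluable, with power of about 36% or 72% in place of more than 90%; this rests on draws of 1/3 per product. Under the likely intent with unblocked orders, the cost is avoidable noise of about 0.07 points, which scales with the assumed drift of 0.5 points per period.

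It should be corrected before randomisation starts, because analysis cannot restore a product that a participant never received. The plan's power statement is not in dispute here.

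**What to change.** Reconcile footnotes d and h and the randomisation and cross-over text in Section 6.1 so that all say the same thing. Suggested wording: *Each participant is allocated once, at Baseline, to one of the six orders of the three products, using permuted blocks so that the orders are balanced. Every product is used in exactly one period.* With blocks of six, 58 participants give 9 or 10 per order; exact equality needs a multiple of six, such as 54 or 60.

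In Section 9.6, add period as a fixed effect in the linear mixed model. A sequence term is optional.

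The cost is a randomisation list, a protocol amendment with the IRB review that Section 12.1 requires, and two model degrees of freedom for period. The sample size and the number of sessions do not change.

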5.0 RECRUITMENT, CONSENT AND ENROLLMENT

5.1 Recruitment

Participants will be recruited through the People Science community, social media channels, including Facebook, Reddit, Instagram, and Google. In addition, People Science will leverage Phylos' community network for recruitment purposes, as deemed appropriate.

Recruitment outreach will consist of IRB approved advertising by email, digital flyers/postcards, and digital marketing channels (email and social media).

The IRB approved study landing page on the People Science website will lead to an IRB approved pre-screening questionnaire to determine individual qualification then collect participant first and last name, email, phone number, and zip code of qualified individuals. New leads will receive further instructions by email to determine qualification and continue through the enrollment process.

5.2 Consent

Virtual electronic informed consent, including a study specific privacy authorization and the California Experimental Subject's Bill of Rights will be provided to participants through a HIPAA compliant cloud-based platform to obtain electronic consent that will ensure that the consenting process follows all required elements (see Section 7.0). A digital copy of the signed consent will be stored with the participant's profile in the study data platform which is the same technology used for electronic consent.

5.3 Enrollment

Eligible participants who provide virtual electronic consent will be automatically registered into the study by the data platform (see Section 12.6).

6.0 STUDY PROCEDURES

6.1 Study Overview

Upon initial qualification, the participant will receive an email with study onboarding information including instructions to complete study assessments, as required. These study assessments can be accessed via the Chloe mobile app available on Apple iOS and Android devices. The participant's activities are as follows:

Screening Day -14 to Day 0:

- Complete the Informed Consent
- Complete Demographics, Medical History and Concomitant medications, including current cannabis use information (frequency, route, any previous adverse reactions from taking cannabis and tolerance in taking at least 5mg THC previously)
- Eligibility Confirmation and Enrollment

Baseline Day 1 to Day 14:

- Provide preferred delivery address for product delivery during Baseline
- Random assignment to either Study Product, THC-Only Product, or Placebo Group
- MEFA Questionnaire
- Receipt of study products within 2 weeks of eligibility confirmation
 - Participants will be asked daily if they have received their study product delivery
 - Once they confirm receipt, they will be advised on the product use period start date

Product Use Period (Up to 21 days):

- *The Participant will be randomized into either Study Product, THC-Only Product, or Placebo Group upon enrollment*

- *The Participant will be crossed-over twice into the Study Product, THC-Only Product, or Placebo Group once they have completed 3 product use sessions during the first and second product use periods*
- *The Participant will complete a total of 9 product use sessions between Study Product, THC-Only Product, and Placebo groups across a maximum of 21 days*
- *The Study Product will contain 10mg THCV + 5mg THC in the form of a single gummy.*
- *If the participant cannot tolerate or is not comfortable with 10mg THC based on cannabis use information collected at screening, the participant may opt to cut the gummy in half and be advised to use the same dose for all product use days for the duration of the study.*

Period 1: Up to 7 days

- After 3 product use sessions:
 - Daily survey questions regarding motivation, level of energy, focus and appetite
 - At the end of Period 1:
 - MEFA Questionnaire and Adverse Event Reporting

Crossover:

- Upon completion of Period 1, participants will cross-over to either the Study Product, THC-Only Product, or Placebo group for up to 7 days.

Period 2: Up to 7 days

- After 3 product use sessions:
 - Daily survey questions regarding motivation, level of energy, focus and appetite
 - At the end of the Period 2:
 - MEFA Questionnaire and Adverse Event Reporting

Crossover:

- Upon completion of Period 2, participants will cross-over to either the Study Product, THC-Only Product, or Placebo group for up to 7 days.

Period 3: Up to 7 days

- After 3 product use sessions:
 - Daily survey questions regarding motivation, level of energy, focus and appetite
 - At the end of the Period 3:
 - MEFA Questionnaire and Adverse Event Reporting

End of Study:

- Experience Survey
- Adverse Event Reporting

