1.0 OBJECTIVES AND ENDPOINTS

| Objectives | Endpoints/ Measurements |
|---|--|
| Primary Objective | |
| To observe the effect of various cannabinoid-containing products on motivation. | Change in average motivation score by 1 point as measured by a 10-point visual analogue rating scale (VAS) collected between the cannabinoid products and placebo use sessions. |
| Secondary Objective | |
| To observe the effect of cannabinoid products on energy level, focus, and appetite. | Change in average score by 1 point as measured by a 10-point visual analogue rating scale (VAS) between the cannabinoid products and placebo use sessions. |
| Exploratory Objective | |
| To observe changes in overall symptoms and quality of life. To identify improvements for future participant centered study designs using participant feedback. | Changes in overall symptoms and quality of life to be assessed based on MEFA questionnaire responses. Evaluation of study participant experiences based on the experience survey. This may include design and use of app-based data collection tools. |

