2.0 INTRODUCTION: BACKGROUND INFORMATION & SCIENTIFIC RATIONALE

2.1 Introduction/Rationale for Development

Tetrahydrocannabivarin (THCV) is a rare cannabinoid and is a homologue of THC that differs only in the length of the alkyl side chain (3C vs 5C, respectively). Pre-clinical and clinical trials have shown that THCV has medical potential as a neuroprotectant, anti-inflammatory, anti-anxiety, and most notably as a therapeutic to improve glycemic control in type 2 diabetic patients.

Several THCV products are available in states with recreational cannabis. Anecdotal reports from adult cannabis users indicate that THCV provides an energizing, focusing and euphoric high—while still creating a lucid, uplifting experience. Additionally, unlike THC-dominant products, THCV was not reported to increase appetite. Other anecdotal comments referring to increased ability to focus for long periods of time and being more active were common.

Given anecdotal evidence, which shows that THCV is activating and improving focus, this provides rationale and justification to conduct a clinical research study to further test and

understand whether THCV improves motivation, focus, level of energy, and does not stimulate appetite in healthy adults.

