3.2 Eligibility

Participants must meet all of the following criteria on screening to be considered eligible to participate in the study:

Inclusion Criteria

1. Healthy adults age \geq 21 years old
2. Work / study / play in an environment that requires focus
3. Able to read and understand English
4. Able to read, understand, and provide informed consent
5. Able to use a personal smartphone device and download Chloe by People Science
6. Able to complete study assessments over the course of up to 14 days
7. Familiar with the use of cannabis and its effects
8. Able to tolerate at least 5mg THC
9. Willingness to abstain from use of any THC containing products during study product use days
10. Willingness to abstain from use of alcohol during study product use days

11. Greater Los Angeles area residents only

Exclusion Criteria

1. Participants who do not have a smartphone and/or internet access
2. Any known adverse effects from taking cannabis
3. Concomitant Therapies: Currently taking medication for ADHD or psychotropic medications
4. Other Illnesses or Conditions: Participants who have the following co-morbidities are excluded:
 - a. History or currently undergoing product use for substance abuse disorders
 - b. Currently pregnant, planning to become pregnant within the next month, or breastfeeding
 - c. Allergies to formulation ingredients
 - d. Current or prior psychotic disorder
 - e. Immunosuppressive product uses, including organ transplant participants, active immunotherapy for cancer product use
 - f. Any condition that is considered by investigator to be a contraindication to cannabis (e.g. specific drug-use interaction, unstable cardiac arrhythmia)

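### The half-gummy rule in section 6.1 turns on 10 mg THC, but the only product with a stated content holds 5 mg THC; confirm both active products' THC content and align the rule.

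*Combined protocol and SAP*

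**What the plan says.** All of the text at issue is in the combined protocol and SAP.

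- **Product content (6.1):** "The Study Product will contain 10mg THCV + 5mg THC in the form of a single gummy".
- **Half-gummy condition (6.1, next bullet):** "If the participant cannot tolerate or is not comfortable with 10mg THC based on cannabis use information collected at screening". Such a participant has the option of cutting the gummy in half and is to "be advised to use the same dose for all product use days for the duration of the study".
- **Eligibility (3.2, inclusion criterion 8):** "Able to tolerate at least 5mg THC".
- **Screening information (6.1):** frequency and route of cannabis use, previous adverse reactions, and "tolerance in taking at least 5mg THC previously".
- **Sessions (6.1):** "a total of 9 product use sessions between Study Product, THC-Only Product, and Placebo groups".
- **THC-Only Product:** named throughout, but its THC content is not given.
- **Comparisons:** the primary endpoint in 1.0 is a difference in motivation score "collected between the cannabinoid products and placebo use sessions". Section 9.1 has the primary and secondary outcomes compared across all three groups, and 9.6 also tests differences among them.

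**The concern.** Two adjacent bullets in a dosing instruction do not agree. One gives the gummy 5 mg THC; the other decides who may halve it by reference to 10 mg THC. Nothing elsewhere in the document reconciles them.

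The study is remote and participants dose themselves, so they and the study staff must act on this sentence as written. What it means for them depends on which figure is wrong. If the threshold is wrong, people who tolerate the whole gummy's THC are offered a reduced dose, and a reduced dose taken in every session is not the product under study. If the content is wrong or incomplete, the error runs the other way: some sessions may deliver more THC than the participant was screened for.

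Interpretation is also at stake. Section 2.1 says the study is meant to "understand whether THCV improves motivation, focus, level of energy, and does not stimulate appetite in healthy adults". The comparison of Study Product with THC-Only bears on THCV itself only if the reader knows how much THC each product carries.

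**Working it through.** The plan gives no derived figure to reproduce. The check sets every THC amount in the document side by side and then works through the possible readings.

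**Inputs**

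| Item | Amount | Place |
|---|---|---|
| Study Product gummy | 10 mg THCV + 5 mg THC | 6.1 |
| Half-gummy threshold | 10 mg THC | 6.1, next bullet |
| Eligibility | at least 5 mg THC tolerated | 3.2, criterion 8 |
| Screening item | at least 5 mg THC tolerated previously | 6.1, Screening |
| THC-Only Product | not stated | – |

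**Step 1. Size of the mismatch.** Threshold / stated THC content = 10/5 = 2. Threshold / eligibility floor = 10/5 = 2. The threshold is the only 10 mg THC figure; the other 10 mg in 6.1 is THCV.

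**Step 2. Doses if the content line is right.** Half gummy = content / 2: 10/2 = 5 mg THCV and 5/2 = 2.5 mg THC. With 9/3 = 3 sessions per product, a participant's Study Product total is 3 × 10 = 30 mg THCV and 3 × 5 = 15 mg THC with whole gummies, or 15 mg and 7.5 mg with halves. By criterion 8, everyone enrolled tolerates at least 5 mg THC. The people caught by the tolerance condition are then those who tolerate 5 mg or more but less than 10 mg, all of whom already tolerate the Study Product's full THC.

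**Step 3. Doses if a product holds 10 mg THC.** A whole unit gives 10 mg, twice the 5 mg asked about at screening. Half gives 10/2 = 5 mg, equal to the eligibility floor. Because halving is only an option, someone whose tolerance is shown only to 5 mg could take the full 10 mg.

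**Step 4. Readings that the text leaves open**

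| Reading of the 10 mg | Consequence |
|---|---|
| Slip for 5 mg THC | The tolerance condition is empty, because criterion 8 already requires 5 mg; only comfort remains |
| Slip for 10 mg THCV | The rule turns on THCV, for which no tolerance item is listed at screening |
| Content line wrong, Study Product holds 10 mg THC | Step 3 applies to Study Product sessions |
| Strength of the THC-Only Product | Step 3 applies to THC-Only sessions, since the chosen dose is meant to hold on all product use days; the two active products then differ by 10 − 5 = 5 mg THC as well as by 10 mg THCV |

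**Step 5. Can the rule be applied from what is collected?** Only in part. Frequency, route and past reactions give some indication, and the comfort condition is the participant's own judgement. The one tolerance item listed is at 5 mg, so it does not separate people above and below 10 mg.

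**The case against.** The strongest reply is that the 10 mg may be the THC-Only strength. The half-dose advice covers all product use days, so a threshold set at the highest THC exposure would make sense and the bullets would not conflict. That stands as a possibility, and it is why the point says only that no product *with a stated content* holds 10 mg. It does not remove the need for a correction: the sentence speaks of the gummy immediately after giving the Study Product's content, and on this reading a twofold THC difference between the active products goes unstated.

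A second reply is that this is a one-figure slip that errs on the cautious side, and so is minor. With the gummy as stated, the rule does only let people take less. But that comfort depends on the content line being right, which the document does not settle.

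Three stronger readings are tempting and are not supported:

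- **A calculable fall in average dose.** If a share h of participants halved, the mean dose would be 1 − h/2 of the stated dose; an assumed h of 25% gives 87.5%. That counts everyone who halves. The option is also open to anyone not comfortable and would continue under a corrected threshold, so only the extra halving belongs to the error. The documents give neither quantity.
- **Confounded product comparisons or lost power.** Participants who halve are advised to keep one dose throughout. If they do, their own product contrasts are made at a constant fraction. The sample-size statement in 9.6 does not involve dose.
- **An issue outside the main endpoints.** A reader might suppose that the THC-Only content matters only for a side comparison. Section 1.0 refers to cannabinoid products in the plural, and 9.1 places THC-Only among the three groups compared for the primary and secondary outcomes.

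**Conclusion.** The inconsistency is real and should be fixed. A decision threshold in a self-dosing rule is twice the THC content of the only product whose content is given, and twice the tolerance used for eligibility and screening. The documents do not show which figure is wrong.

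The per-person consequence is bounded by the arithmetic above. With the stated gummy, someone who tolerates its full THC may take 5 mg THCV + 2.5 mg THC in place of 10 mg + 5 mg. If a product holds 10 mg THC, someone screened only for 5 mg may take 10 mg. These are alternatives that depend on the true content, and neither is asserted as fact. How many participants would be affected, and by how much the average dose or effect would shift, cannot be estimated from the documents.

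**What to change.** The sponsor confirms the THC content of both active products and aligns 6.1 with it.

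- **If neither product exceeds 5 mg THC:** replace the 10 mg THC threshold with the whole gummy's content (10 mg THCV + 5 mg THC) and base the option on comfort alone, since criterion 8 already covers tolerance of 5 mg THC.
- **If either product holds 10 mg THC:** correct or add its content statement, ask about 10 mg tolerance at screening, and require the half dose throughout for participants who have not tolerated 10 mg. Changing the number while leaving the half dose optional would not protect them.
- **In either case:** state the THC-Only Product's THC content in the same edit, because that product enters the primary, secondary and 9.6 comparisons.

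The cost is a wording amendment submitted to the IRB, as section 12.1 requires for any protocol change, plus one screening question only if a product holds 10 mg THC. The sample size and the planned analyses do not change.
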